**10.3.5.2 Tables for Laboratory Abnormalities**

The pre-defined intensity thresholds for laboratories abnormalities are shown in [Table 10.4](#).

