**Table 10.4: Intensity thresholds for laboratory abnormalities**

Endpoint	Mild (Grade 1)	Moderate (Grade 2)	Severe (Grade 3)
Above normal WBC – cell/mm 	10,800 – 15,000	15,001 – 20,000	≥ 20,001
Below normal WBC – cell/mm 	2,500 – 3,500	1,500 – 2,499	≤ 1,499
Hemoglobin (Female) – gm/dL	11.0 – 12.0	9.5 – 10.9	≤ 9.4
Hemoglobin (Female) (Change from baseline value) – gm/dL	Any decrease – 1.5	1.6 – 2.0	≥ 2.1
Hemoglobin (Male) – gm/dL	12.5 – 13.5	10.5 – 12.4	< 10.5
Hemoglobin (Male) (change from baseline value) – gm/dL	Any decrease – 1.5	1.6 – 2.0	≥ 2.1
Platelets decreased – cell/mm 	125,000 – 140,000	100,000 – 124,000	≤ 99,000
Absolute neutrophil decrease – cell/mm 	1,500 – 2,000	1,000 – 1,499	< 999
Absolute lymphocyte decrease – cell/mm 	750 – 1,000	500 – 749	< 499
Absolute eosinophil – cell/mm 	650 – 1500	1501 - 5000	> 5000
Sodium – Hyponatremia – mEq/L	132 – 134	130 – 131	< 130
Sodium – Hypernatremia – mEq/L	144 – 145	146 – 147	> 148
Potassium – Hyperkalemia – mEq/L	5.1 – 5.2	5.3 – 5.4	> 5.4
Potassium – Hypokalemia – mEq/L	3.5 – 3.6	3.3 – 3.4	< 3.3
Blood Urea Nitrogen (BUN) – mg/dL	23 – 26	27 – 31	> 31 or require dialysis
Creatinine – mg/dL	1.5 – 1.7	1.8 – 2.0	≥ 2.1 or requires dialysis
Glucose – Hyperglycemia (random) – mg/dL	110 - 125	126 - 200	> 200
Total protein – Hypoproteinemia – g/dL	5.5 – 6.0	5.0 – 5.4	< 5.0
LFT (ALT, AST) (Increase by factor)	1.1 – 2.5 x ULN	2.6 – 5.0 x ULN	≥ 5.1 ULN
Alkaline phosphate (Increase by factor)	1.1 – 2.0 x ULN	2.1 – 3.0 x ULN	≥ 3.1 ULN
Bilirubin – with any increase in LFT (Increase by factor)	1.1 – 1.25 x ULN	1.26 – 1.5 x ULN	≥ 1.51 ULN
Bilirubin – with normal LFT (Increase by factor)	1.1 – 1.5 x ULN	1.6 – 2.0 x ULN	≥ 2.1 ULN

Endpoint	Mild (Grade 1)	Moderate (Grade 2)	Severe (Grade 3)
PT – increase by factor (prothrombin time)	1.0 – 1.10 x ULN	1.11 – 1.20 x ULN	1.21 – 1.25 x ULN
PTT – increase by factor (partial thromboplastin time)	1.0 – 1.2 x ULN	1.21 – 1.4 x ULN	1.41 – 1.5 x ULN
Urine - glucose	Trace	1+	2+
Urine - protein	Trace	1+	2+
Urine – blood (microscopic - RBCs per high power field (rbc/hpf)	1 - 10	11 - 50	> 50 and/or gross blood

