4.4.1.1 Solicited Reactions

4.4.1.1.1 Daily Intensity

All daily records for solicited reactions will be derived into daily intensity according to the following classification: None, Grade 1, Grade 2, Grade 3, or Missing.

For measurable injection site reactions:

- None: > 0 to < 25 mm
- Grade 1: ≥ 25 to ≤ 50 mm
- Grade 2: ≥ 51 to ≤ 100 mm
- Grade 3: > 100 mm

For Fever:

- None: $< 38.0^{\circ}\text{C}$ or $< 100.4^{\circ}\text{F}$
- Grade 1: $\geq 38.0^{\circ}\text{C}$ to $\leq 38.4^{\circ}\text{C}$ or $\geq 100.4^{\circ}\text{F}$ to $\leq 101.1^{\circ}\text{F}$
- Grade 2: $\geq 38.5^{\circ}\text{C}$ to $\leq 38.9^{\circ}\text{C}$ or $\geq 101.2^{\circ}\text{F}$ to $\leq 102.0^{\circ}\text{F}$
- Grade 3: $\geq 39.0^{\circ}\text{C}$ or $\geq 102.1^{\circ}\text{F}$

For the derivation of daily intensities, the following sequential steps will be applied:

- 1) Solicited reactions (except fever/pyrexia) with an Investigator presence recorded as “No” and with all daily records missing then all daily intensities will be derived as “None”.
- 2) For non-measurable solicited reactions, daily intensities will correspond to daily records reported in the clinical database. For measurable solicited reactions the daily measurements reported in the clinical database will be converted based upon the intensity scales defined in the protocol; this assumes a reaction that is too large to measure (non-measurable, “NM”) is Grade 3. Note: the intensity could be considered “None” (not a reaction) in the analysis

despite being considered a reaction by the Investigator (eg, swelling measurement > 0 mm but < 25 mm in adults).

Note: The maximum intensity on the ongoing period is derived from the record of the maximum intensity/measurement after the end of the solicited period following the rule described above.

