4.4.1.4 Laboratory Test Results

Biological safety tests (biochemistry, hematology, urinalysis, and coagulation) will be performed at the local laboratory. Biological endpoints will be assessed on samples taken at screening and D09 for all participants, D30 (only applicable for Sentinel Cohort and Cohort 2), and unscheduled visits based on Investigator's judgment, in cases of abnormal safety laboratory results.

The parameters to be evaluated are detailed in Table 10.1 of the protocol.

Endpoints will be defined as either within or outside normal range. Normal ranges for each endpoint will be provided by the study center. The biological safety information will be entered by the site staff in the appropriate CRF forms along with units and normal ranges. In case of out-of-range values, specific endpoints may be rechecked, and additional biological parameters may be evaluated, based on the Investigator's judgement. This complementary safety information will also be entered by the site staff in the appropriate CRF forms along with units and normal ranges.

Any change in the testing equipment using different ranges should be reported on an ongoing basis to the Sponsor so that any value can be interpreted at a given time against the appropriate range of values.

Biological safety endpoints will be assessed on whether or not they reach the pre-defined intensity levels (Grade 1, 2, or 3) for analytes with applicable toxicity grading, as specified in the protocol. Table 10.4 of the protocol contains the pre-defined intensity scales according to which the biological safety parameters will be assessed. If at least 1 of these intensity levels is reached, the Investigator will evaluate the clinical significance of the results and report clinically significant abnormal values as AEs in the CRF.

If an endpoint reaches the pre-defined intensity threshold but is within the normal range provided by the study center, it will be treated as not reaching the intensity threshold.

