5.1.1.2 Statistical Methods for Primary Safety Objective

The following safety parameters will be used for the evaluation of safety. Additional parameters may be displayed as appropriate.

Solicited Reactions

Number and percentage of participants with:

- Presence of solicited injection site reactions and systemic reactions occurring up to 7 days after injection
- Each solicited reaction according to time of onset, maximum intensity, and number of days of occurrence over the solicited period

Unsolicited Events and Reactions

Number and percentage of participants with:

- Any unsolicited immediate systemic event in the 30 minutes after injection
- Any unsolicited event and reaction (using the current MedDRA version) 21 days after injection
- Any unsolicited event/reaction according to time of onset, maximum intensity, and duration

SAEs

Number and percentage of participants with:

- Any SAE within 21 days after injection and throughout the entire study according to SOC and PT, seriousness, and outcome

AESIs

Number and percentage of participants with:

- Any AESI within 21 days after injection and throughout the entire study according to SOC and PT, seriousness, and outcome

MAAEs

Number and percentage of participants with:

- Presence of MAAEs within 21 days after injection and throughout the entire study

Laboratory tests

- Presence of out-of-range biological test results up to 8 days post-last dose (ie, up to D09 for Cohort 1 and up to D30 for Sentinel Cohort and Cohort 2)
- Summary of toxicity grade shift from baseline

For descriptive purposes, the statistics presented in [Table 5.1](#) will be produced for the above safety parameters for each intervention group and each age group. The same dose-level group in Sentinel Cohort and Cohort 2 will also be pooled for analysis.

Harm analysis

Harm analysis assessed based on split of COVID-19 case will be assessed based on Safety Analysis Set (SafAS) at the time of the final analysis. Participants will be analyzed according to the study intervention they received. For the assessment, all dose-level arms will be pooled, and all placebo arms will be pooled as well.

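### Table 10.4 caps Grade 3, its top grade, at 1.25 x ULN for PT and 1.5 x ULN for PTT, and neither document says how higher results are graded

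*Protocol*

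**What the plan says.** Protocol 10.3.5.2 introduces the laboratory grades with the words "The pre-defined intensity thresholds for laboratories abnormalities are shown in" Table 10.4. The table has 27 rows and three grade columns, and Grade 3 is the highest. The two coagulation rows, as multiples of the upper limit of normal (ULN), are:

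| Test | Grade 1 | Grade 2 | Grade 3 |
|---|---|---|---|
| PT | 1.0 to 1.10 | 1.11 to 1.20 | "1.21 – 1.25 x ULN" |
| PTT | 1.0 to 1.2 | 1.21 to 1.4 | 1.41 to 1.5 |

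SAP 4.4.1.4 adopts this table without a scale of its own. It says that Table 10.4 "contains the pre-defined intensity scales according to which the biological safety parameters will be assessed", and it describes the assessment as whether a result reaches a level. Its one override begins "If an endpoint reaches the pre-defined intensity threshold but is within the normal range provided by the study center"; such a result is treated as not reaching the threshold. Among the laboratory outputs for the primary safety objective, SAP 5.1.1.2 lists a "Summary of toxicity grade shift from baseline".

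**The concern.** A top grade needs no outer limit, because there is no higher category to receive what lies beyond it. The other rows expressed as multiples of ULN (ALT/AST, alkaline phosphatase and both bilirubin rows) leave Grade 3 open. PT and PTT do not, so a program that copies the printed ranges gives no grade to any result past the cap.

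The error would run in one direction: it would remove only the most abnormal PT and PTT results from the Grade 3 cells, and keep the milder ones. A shift table exists to show movement from normal at baseline to an abnormal grade after vaccination, and here the largest movements would be the ones missing.

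**Working it through.** The plan gives no figure to reproduce. The check is to grade the same values under the two readings that the text allows.

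**Inputs.** The PT and PTT limits from Table 10.4, as shown above. Let r be the result divided by ULN.

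**Reading A, as printed.** Grade g applies if lower limit of g ≤ r ≤ upper limit of g. If no range contains r, there is no grade.

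**Reading B, limit reached.** The grade is the highest g for which r ≥ lower limit of g.

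| Test | r | Reading A | Reading B |
|---|---|---|---|
| PT | 1.05 | 1 | 1 |
| PT | 1.15 | 2 | 2 |
| PT | 1.23 | 3 | 3 |
| PT | 1.25 | 3 | 3 |
| PT | 1.26 | none | 3 |
| PT | 1.30 | none | 3 |
| PT | 2.0 | none | 3 |
| PTT | 1.15 | 1 | 1 |
| PTT | 1.30 | 2 | 2 |
| PTT | 1.45 | 3 | 3 |
| PTT | 1.5 | 3 | 3 |
| PTT | 1.51 | none | 3 |
| PTT | 1.6 | none | 3 |
| PTT | 2.0 | none | 3 |

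At these values the readings agree up to the cap and differ everywhere above it.

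**Is the closed range usual in this table?** Four of the 27 rows do not leave Grade 3 open: PT, PTT, urine glucose and urine protein. So 27 − 4 = 23 rows are open-ended. The two urine rows give a single dipstick level (2+). Protocol Table 10.1 does not state the dipstick scale, so nothing can be concluded about values above 2+.

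**Does another rule catch these results?** The normal-range override cannot apply, because a result above 1.25 x ULN or 1.5 x ULN is outside the normal range by definition. SAP 5.3.3 deals with values reported with an inequality sign, and only for descriptive statistics. Neither rule assigns a grade.

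**What does not depend on the grade?** For the out-of-range endpoint, SAP 4.4.1.4 says "Endpoints will be defined as either within or outside normal range". A PT of 1.30 x ULN is counted there under either reading.

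**The case against.** The strongest reply is that the documents already point to the sensible answer. Protocol 10.3.5.2 speaks of thresholds, SAP 4.4.1.4 of levels being reached, and exclusion criterion E20 of Grade 1 or greater, which treats the grades as ordered. A careful programmer would probably code anything above 1.21 x ULN for PT, or 1.41 x ULN for PTT, as Grade 3. SAP 5.7 also refers to a Tables, Listings and Figures document that may contain the rule. All of this stands, and it keeps the point minor. It does not remove it: the printed range and the implied rule give different grades, SAP 4.4.1.4 also calls the table a scale, and neither document states which governs.

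SAP 4.4.1.1.1 might be cited as a contrast, since for solicited reactions "this assumes a reaction that is too large to measure" is Grade 3. The comparison is weak. That rule codes a non-numeric entry on a scale whose Grade 3 is already open above 100 mm. It does not extend a closed range.

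A reader might infer that the whole table needs a general limit-reached rule, because some other rows have small gaps between adjacent grades. The printed table does not support one. Twelve rows print Grade 3 with a strict < or >. An inclusive rule would move nine boundary values from a printed Grade 2 to Grade 3, among them potassium 5.4, sodium 130 and BUN 31. A rule written for decreases would also misfit the two hemoglobin change rows, which print falls as positive numbers.

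A reader might also infer that extreme coagulation results would go unseen. The documents do not support that: the out-of-range endpoint counts them, and Protocol 8.3.4 requires the investigator to review each laboratory report whatever the grade.

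**Conclusion.** The point holds as a minor defect. Taken as printed, Table 10.4 gives no grade to PT above 1.25 x ULN or PTT above 1.5 x ULN. The grade-shift summary would then lose its most abnormal coagulation results from the Grade 3 cells. The loss occurs only if the program follows the printed ranges and the Tables, Listings and Figures document has no overriding rule; neither could be checked.

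The number of participants affected is unknown. It is probably small, since these are healthy adults screened on coagulation tests. E20 is not firm evidence of this, because it relies on the same grades and, read literally, has the same gap.

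It would be too narrow to say that only the shift summary is exposed. Grade 3 laboratory results also enter the Sentinel Cohort alert criteria (Protocol 8.4.1 and 8.4.2) and the halting criteria (8.4.3). SAP section 1 records that vaccination and enrollment were ended from 27 September 2021, so the final analysis is what remains to be settled. The passages should still be reconciled with the two rows. No clinical threshold is proposed here.

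**What to change.** Add one sentence to SAP 4.4.1.4 and make the grading program match:

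> For the grade summaries, PT and PTT results above the printed upper end of the Grade 3 range in Table 10.4 are counted as Grade 3.

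Keep the existing rule for results within the site's normal range. Leave every other row as printed, including the strict inequalities. If the Tables, Listings and Figures document already contains this rule, cite it in 4.4.1.4 instead.

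Separately, the sponsor should confirm how the PT and PTT rows were read in Protocol 8.4.1, 8.4.2, 8.4.3 and E20, and reconcile those passages with the table.

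The cost is one sentence and a program check before the final analysis. The only downside is possibly a few more Grade 3 results in one descriptive table.

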## 10.4 Appendix: Collection of Pregnancy Information

### **DEFINITIONS:**

#### ***Woman of Childbearing Potential (WOCBP)***

A woman is considered fertile following menarche and until becoming post-menopausal unless permanently sterile (see below).

If fertility is unclear (eg, amenorrhea in adolescents or athletes) and a menstrual cycle cannot be confirmed before first dose of study intervention, additional evaluation should be considered.

#### ***Women in the Following Categories are not Considered WOCBP***

- 1) Premenarchal
- 2) Premenopausal female with 1 of the following:
  - Documented hysterectomy
  - Documented bilateral salpingectomy
  - Documented bilateral oophorectomy

For individuals with permanent infertility due to an alternate medical cause other than the above, (eg, mullerian agenesis, androgen insensitivity), Investigator discretion should be applied to determining study entry.

Note: Documentation can come from the site personnel's: review of the participant's medical records, medical examination, or medical history interview.

- 3) Post-menopausal female
  - A post-menopausal state is defined as no menses for 12 months without an alternative medical cause.
    - A high follicle stimulating hormone (37) level in the post-menopausal range may be used to confirm a post-menopausal state in women not using hormonal contraception or hormonal replacement therapy (HRT). However, in the absence of 12 months of amenorrhea, confirmation with more than one FSH measurement is required.
  - Females on HRT and whose menopausal status is in doubt will be required to use one of the non-estrogen hormonal highly effective contraception methods if they wish to continue their HRT during the study. Otherwise, they must discontinue HRT to allow confirmation of post-menopausal status before study enrollment.

### **COLLECTION OF PREGNANCY INFORMATION**

The collection period of pregnancy information will correspond at least to the period during which the participant is requested to be under contraception. (according to protocol: effective method of contraception or abstinence from at least 4 weeks prior to the first vaccination until at least 12 weeks after the last vaccination). If there are any pregnancy during this period, follow-up should be conducted up to delivery: this will be covered by the 12-month surveillance of the study.

***Female Participants who Become Pregnant***

- The Investigator will collect pregnancy information on any female participant who becomes pregnant while participating in this study. The initial information together with the contraceptive method if any will be recorded on the appropriate form and submitted to the Sponsor within 1 month of learning of a participant's pregnancy.
- The participant will be followed to determine the outcome of the pregnancy. The Investigator will collect follow-up information on the participant and the neonate and the information will be forwarded to the Sponsor. Generally, follow-up will not be required for longer than 6 to 8 weeks beyond the estimated delivery date but will be in accordance with local regulations. Any termination of pregnancy will be reported, regardless of fetal status (presence or absence of anomalies) or indication for the procedure.
- While pregnancy itself is not considered to be an AE or SAE, any pregnancy complication or elective termination of a pregnancy for medical reasons will be reported as an AE or SAE.
- A spontaneous abortion (occurring at < 22 weeks gestational age) or still birth (occurring at > 22 weeks gestational age) is always considered to be an SAE and will be reported as such.
- Any post-study pregnancy related SAE considered reasonably related to the study intervention by the Investigator will be reported to the Sponsor as described in [Section 8.4.7](#). While the Investigator is not obligated to actively seek this information in former study participants, he or she may learn of an SAE through spontaneous reporting.
- In case of pregnancy during the primary series and if at least 1 dose of the study vaccine(s) has been administered, the participant will not be discontinued from the study, but no further vaccination will be administered until after delivery (if applicable and still within the study vaccination window). However, the participant will be followed for safety assessment (and may be followed for immunogenicity assessment, if applicable).
- If primary series have been completed and the delivery occurs between the primary series and the booster, the booster dose can be administered. However, if vaccination is a contraindication for lactation (ie, live-attenuated vaccine), the participant may not be vaccinated with a booster dose.

## 10.5 Appendix: AESIs

### Protocol-Specified AESIs

- Anaphylactic reactions
- Generalized convulsion
- Guillain-Barré Syndrome (GBS)
- Acute disseminated encephalomyelitis (ADEM)
- Thrombocytopenia
- Vasculitides
- NOCMCs

### AESIs Related to SARS-CoV-2 Infection and COVID-19 Disease

#### **Immunologic**

- Enhanced disease following immunization

#### **Respiratory**

- Acute respiratory distress syndrome

#### **Cardiac**

Acute cardiac injury including:

- Microangiopathy
- Heart failure and cardiogenic shock
- Stress cardiomyopathy
- Coronary artery disease
- Arrhythmia
- Myocarditis, Pericarditis

#### **Endocrine**

- Pancreatitis
- Subacute thyroiditis

#### **Hematologic**

Coagulation disorder

- Deep vein thrombosis
- Pulmonary embolus
- Cerebrovascular stroke
- Limb ischemia
- Hemorrhagic disease

#### **Musculoskeletal**

- Rhabdomyolysis

**Renal**

- Acute kidney injury

**Gastrointestinal**

- Liver injury

**Neurologic**

- GBS
- Anosmia, Ageusia
- Meningoencephalitis

**Dermatologic**

- Chilblain-like lesions
- Single organ cutaneous vasculitis
- Erythema multiforme

**10.6 Appendix: Risk-based Approach**

ICH E6-R2 guideline for GCP is introducing the « risk-based approach » concept which permits to focus efforts on what is critical for a study and most specifically on Critical Data and Critical Processes. Critical data and processes are defined for the study with associated risks in the Study Risk Management Plan.

## 10.7 Appendix: Abbreviations

2P	double proline
Ab	antibody
ADEM	acute disseminated encephalomyelitis
AE	adverse events
AESI	adverse event of special interest
AIT	Additional Immunological Tests
ALT	alanine aminotransferase
AST	aspartate aminotransferase
AR	adverse reactions
BL	blood sample (#)
CDISC	Clinical Data Interchange Standards Consortium
CI	confidence interval
CIOMS	Council for International Organizations of Medical Sciences
CMI	cell-mediated immunity
CRF	case report form
CS-ESDR	Complete Sentinel Early Safety Data Review
D	Day
DC	diary card
DMC	Data Monitoring Committee
DNA	deoxyribonucleic acid
ECG	electrocardiogram
ECLIA	electrochemiluminescence immunoassay
ELISA	enzyme-linked immunosorbent assay
ESDR	Early Safety Data Review
FAS	Full Analysis Set
FDA	Food and Drug Administration
FSH	follicle stimulating hormone
GBS	Guillain-Barré Syndrome
GCI	Global Clinical Immunology
GCP	Good Clinical Practice

GDPR	General Data Protection Regulation
GMC	geometric mean concentration
GMT	geometric mean titer
GPV	Global Pharmacovigilance
HA	hemagglutinin
hCG	human chorionic gonadotropin
HCoV	Human Coronavirus
HIPAA	Health Insurance Portability and Accountability Act
HIV	human immunodeficiency virus
HRT	hormonal replacement therapy
IB	Investigator's Brochure
ICF	informed consent form
ICH	International Council for Harmonisation
ICU	intensive care unit
IEC	Independent Ethics Committees
IgG	immunoglobulin G
INR	international normalized ratio
IRB	Institutional Review Boards
IRT	Interactive Response Technology
█	████████████████████
██████	██
LLOQ	lower limit of quantification
LNP	lipid nanoparticle
MAAE	medically attended adverse event
MedDRA	Medical Dictionary for Regulatory Activities
MERS-CoV	Middle East Respiratory Syndrome coronavirus
mRNA	messenger ribonucleic acid
█	████████████████████
██████	██
NAAT	nucleic acid amplification test
NHP	non-human primate
NOAEL	no-observed-adverse-effect level

NOCMC	new-onset chronic medical conditions
OD	optical density
PBMC	peripheral blood mononuclear cell
█	█
PPAS	per-protocol analysis set
PPAS-AIT	per-protocol analysis set for AIT
PPAS-IAS	per-protocol analysis set for immunogenicity
PT	prothrombin time
PTT	partial thromboplastin time
RMO	Responsible Medical Officer
RNA	ribonucleic acid
S	spike
SAE	serious adverse event
SafAS	Safety Analysis Set
SAP	Statistical Analysis Plan
SARS-CoV-2	severe acute respiratory syndrome coronavirus 2
SGOT	Serum Glutamic-Oxaloacetic Transaminase
SGPT	Serum Glutamic-Pyruvic Transaminase
SMT	Safety Management Team
SoA	Schedule of Activities
SUSAR	suspected unexpected serious adverse reactions
TC	telephone call
Th	T-helper cell
VAC	Vaccination (as in Vaccination #)
US	United States
█	█
WOCBP	Woman of Childbearing Potential

